### **Dose Escalation Procedures**

The dose of treatment agent will be escalated in successive cohorts of patients. The starting dose is at dose 0 as shown in table 1. Enroll 3 patients at the dose level and proceed to the next higher dose level with a cohort of 3 patients until at least 1 patient experiences a dose-limiting toxicity (DLT).

DLT is defined as a clinically significant adverse event or abnormal laboratory value assessed as unrelated to disease progression, intercurrent illness, or concomitant medications and meeting the NCI common terminology criteria that are CTCAE Grade 3 or 4.

An adverse event must be clinically significant to define DLT e.g. alopecia, study drug-related fever, electrolyte abnormalities (including K, Na, Cl, HCO3, Mg, Ca) that are < Grade 3 will not define the DLT. Drug-related Grade 3-4 nausea and vomiting not controlled with adequate therapy will be considered DLTs.

If only 1 of 3 patients experiences a DLT at a given dose level, enter 3 additional patients at the current dose level. If only 1 of 6 patients experiences a DLT at a given dose level, proceed to the next higher dose level with a cohort of 3 patients. If at least 2 of 3 or 2 of up to 6 patients experience a DLT at a

given dose level, then the MTD has been exceeded (stopping dose). Once the MTD has been exceeded, treat another 3 patients at the previous dose level if there were only 3 patients treated at that dose level. The MTD is defined as the highest dose level in which 6 patients were treated with at most 1 experiencing a DLT during the 1st cycle.

In summary, our dose escalation plan is as follows: during phase I, the starting dose is 10 mg and dose escalation will follow a 3 + 3 design. After three patients have received 10 mg, if there is no DLT, the next cohort of three patients will receive 25 mg. If there is one DLT in the initial three patients, an additional three patients will be treated at 10 mg. If 2/6 patients experience a DLT at 10 mg, the study will be closed. If less than or equal to 1/6 at 10 mg experience a DLT, we will enroll the next three patients at 25 mg. The maximum dose on this protocol is 25 mg, thus, no further dose escalation will occur. If 1/3 patients at 25 mg experience a DLT, we will enroll three additional patients at 25 mg. If 2/6 experience a DLT, all subsequent patients will receive 10 mg, and that will be the final dose. If less than or equal to 1/6 experience a DLT at 25 mg, the remainder of the patients enrolled will receive 25 mg. If 2/3 or 2/6 patients experience a DLT at the 10 mg dose, the study will be terminated.

Table 1. Dose levels of rituximab

| Dose level        | rituximab |
|-------------------|-----------|
| 0 (starting dose) | 10 mg     |
| 1                 | 25 mg     |

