#### Selection of Patients:

Patients will be eligible for the study if they relapsed and/or refractory CD20+ lymphoid malignancies (all patients beyond complete remission 1 are considered eligible). Upon suspicion of LMD, the patients will be screened for the protocol. The preference at this point will be for the patient to receive a diagnostic lumbar puncture (i.e., no chemotherapy administered). However, if it is deemed necessary to instill conventional chemotherapy (e.g., methotrexate or cytarabine) during the first lumbar puncture, these patients will still be eligible for the protocol. The two groups will be analyzed separately for all outcomes (i.e., patients who received no intrathecal chemotherapy prior to receiving intrathecal rituximab, and patients who received cytarabine or methotrexate before commencing intrathecal rituximab). If a patient had received IT methotrexate or cytarabine and is subsequently enrolled, at least 48 hours should elapse from the administration of methotrexate or cytarabine to the first application of IT rituximab.

Once enrolled, the patients will go on to receive rituximab 10 mg intrathecally twice weekly until 2 consecutive CSF samples are negative for the presence of blast cells 48 hours must elapse between intrathecal rituximab doses. Thereafter, rituximab 10 mg intrathecally will be administered weekly for an additional 4 weeks, followed by intrathecal rituximab 10 mg administered once every other week for an additional 8 weeks.

After the first three patients are enrolled and followed for at least 2 weeks, if no dose limiting toxicity is experienced, all subsequent patients will be given rituximab 25 mg intrathecally on an identical schedule as described above. This dose was identified as the maximum tolerated dose in the phase I study

conducted by Rubenstein and colleagues. If excessive toxicity is noted in the first 3 patients given rituximab 25 mg (with at least two weeks of follow up), we will move back to the 10 mg dose, and that will be the final dose employed going forward.

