### **Statistical Considerations**

The primary outcome of the study will be response rate. Time to recurrence of CNS leukemia and overall survival will be secondary outcomes. Time to recurrence and survival will be considered from the date of CNS relapse diagnosis.

There is no well-defined metric to measure response to treatment in patients with peripheral nerve involvement only. Clinical and radiologic response will be recorded and it is expected that few to no patients with only peripheral nerve involvement will actually be involved and therefore the statistical analysis will not be affected.

A maximum of 25 patients will be enrolled in this phase I/II study, with about 12 patients/year.

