### **Phase I**

First, phase I study is performed to assess the safety of two dose levels for rituximab: 10mg and 25mg. These two dose levels have been previously in a small series (12). A 3+3 design will be used to for dose escalation. Detailed dose escalation rules are described in the following section. A maximum of 12 patients will enroll in the phase I study.

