#### Monitoring Of non-hematological $\geq$ grade 3 toxicities

With the concern of treatment related toxicity, the non-hematological toxicity ( $\geq$ grade 3) will also be closely monitored during the study. Since the 6 patients treated at MTD in phase I will be included for efficacy evaluation in phase II, the toxicity monitoring in phase II start either with the 7th patient or with the 1st patient treated at the MTD.

Denote the probability of toxicity by  $P_E$ . We assume  $P_E \sim \text{beta} (0.6,1.4)$ . Our stopping rule is given by the following probability statement:  $\text{Pr}(P_E > 0.3 \mid \text{data}) > 0.9$ . That is, we will stop the trial if, at any time during the study, we determine that there is more than 90% chance that the toxicity is more than 30%. The study will be stopped early if (The number of non-hematological toxicities being grade 3 or higher)/ (The number of patients evaluated)  $\geq 4/6, 5/8, 6/10, 7/13, 8/15, 9/18, 10/21$ . The operating characteristics are summarized in table 3.

Table 3: Operating characteristics for monitoring of non-hematological  $\geq$ grade 3 toxicities

| True Toxicity Rate | Early Stopping Probability | Median Sample size (interquartile) |
|--------------------|----------------------------|------------------------------------|
| 0.2                | 0.05                       | 22 (22,22)                         |

|     |      |             |
|-----|------|-------------|
| 0.3 | 0.22 | 22 (22, 22) |
| 0.4 | 0.54 | 19 (7, 22)  |
| 0.5 | 0.82 | 7 (6, 17)   |

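### The MTD needs six treated patients, but no rule states the next step after 0/3 DLTs at 25 mg, and the sections disagree on what DLTs in patients 4 to 6 at that dose would do

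*Protocol*

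**What the plan says.** Protocol, Phase I: the "phase I study is performed to assess the safety of two dose levels for rituximab: 10mg and 25mg", using a 3+3 design, and "A maximum of 12 patients will enroll in the phase I study".

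Protocol, Dose Escalation Procedures (same text in the SAP): "The MTD is defined as the highest dose level in which 6 patients were treated with at most 1 experiencing a DLT", counted in the first cycle. After a cohort of three without a DLT, the trial goes to the next level. Two DLTs among three, or among up to six, mean that the MTD has been exceeded; three more patients are then treated at the level below if only three had been treated there.

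The summary at the end of that section names 25 mg as the highest dose. For 25 mg it lists three outcomes:
- 1/3: "If 1/3 patients at 25 mg experience a DLT, we will enroll three additional patients at 25 mg".
- 2/6: "If 2/6 experience a DLT, all subsequent patients will receive 10 mg, and that will be the final dose".
- At most 1/6: the remaining patients receive 25 mg.

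It also ends the study if 2/3 or 2/6 have a DLT at 10 mg.

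Protocol, Selection of Patients: after three patients at 10 mg without a DLT, everyone enrolled later receives 25 mg. The return to 10 mg, as the final dose, is triggered by this condition: "If excessive toxicity is noted in the first 3 patients given rituximab 25 mg".

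Protocol, Phase II and the toxicity monitoring section: patients treated at the MTD in phase I count toward a phase II sample of up to 22. The monitoring section begins "Since the 6 patients treated at MTD in phase I will be included for efficacy evaluation in phase II" and lets monitoring start with either the 7th or the 1st patient at the MTD. Its first stopping boundary is 4/6.

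**The concern.** A 3+3 scheme should give one action for every outcome at every level. Here 0/3 at 25 mg has no stated action. Going up is impossible, expansion to six is prescribed only after 1/3, and the other two listed outcomes already presuppose six patients. Immediately after 0/3 at 10 mg and 0/3 at 25 mg, neither dose has six patients, so neither yet meets the MTD definition on which phase II is built.

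At stake is what happens when DLTs appear in patients 4, 5 and 6 at 25 mg. Depending on the section followed, the same results either reverse the dose or leave it unchanged. That affects the safety of those patients, the dose taken into phase II, and which patients enter the phase II response rate.

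A smaller point: Selection of Patients and the escalation summary call 10 mg the final dose after a fall-back without repeating the earlier instruction to bring 10 mg up to six patients.

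**Working it through.** **Plan's own figures.** Phase I maximum: 2 levels × 6 = 12. The fall-back path with the extra three at 10 mg gives 3 + 6 + 3 = 12. Total: 3 at 10 mg + 22 at 25 mg = 25, the stated cap ("A maximum of 25 patients will be enrolled in this phase I/II study"). All three agree with the documents.

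**Actions after 0/3 at 25 mg, then DLTs in patients 4 to 6**

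| Total DLTs | Dose Escalation Procedures (2 of up to 6) | Selection of Patients (first 3 only) | Phase II boundary (from 4/6) |
|---|---|---|---|
| 0/6 or 1/6 | stay at 25 mg | stay | continue |
| 2/6 or 3/6 | return to 10 mg | stay | continue |

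**Phase II rule at six patients.** Inputs from the toxicity monitoring section: prior Beta(0.6, 1.4); stop if Pr(toxicity > 0.3 | data) > 0.9. With x events in n patients the posterior is Beta(0.6 + x, 1.4 + n − x).
- 2/6: Beta(2.6, 5.4), Pr = 0.52. Continue.
- 3/6: Beta(3.6, 4.4), Pr = 0.80. Continue.
- 4/6: Beta(4.6, 3.4), Pr = 0.94. Stop, matching the stated first boundary.

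After 0/3, at most three events can occur in the next three patients, so 4/6 is out of reach at patient 6. The earliest possible stop is 4/7 (Pr = 0.901). This comparison assumes that the same events count under both rules.

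**How often.** The documents give no DLT rate, so p is assumed.

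0/3 at both doses, with the same p at each: (1 − p)^6.
- p = 0.1: 0.9^6 = 0.531
- p = 0.2: 0.8^6 = 0.262

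At 25 mg:
- A = P(0/3) = (1 − p)³
- B = P(at least 2 DLTs in the next 3) = 3p²(1 − p) + p³
- A × B = probability of the conflicting sequence in a trial that reaches 25 mg

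| p at 25 mg | A | B | A × B |
|---|---|---|---|
| 0.1 | 0.729 | 0.028 | 0.020 |
| 0.2 | 0.512 | 0.104 | 0.053 |
| 0.3 | 0.343 | 0.216 | 0.074 |
| 0.4 | 0.216 | 0.352 | 0.076 |
| 0.5 | 0.125 | 0.500 | 0.063 |

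**Comparison path: closure at 10 mg** (2 or more of 3, or 1/3 and then at least one more in the next three): 3p²(1 − p) + p³ + 3p(1 − p)² × [1 − (1 − p)³].
- p = 0.1: 0.028 + 0.243 × 0.271 = 0.094
- p = 0.2: 0.104 + 0.384 × 0.488 = 0.291

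**The case against.** The strongest reply is that the intent can be recovered. The 2-of-up-to-6 rule is not conditional on a first 1/3, so it literally covers 0/3 followed by two DLTs. The phase I maximum of 12, the monitoring section's reference to six, and the outcome of at most 1/6 (which includes 0/6) all point to a six-patient phase I count. This has force: six is probably what was meant. It does not remove the conflict, because no stated branch enrols patients 4 to 6 as phase I patients after 0/3, Selection of Patients limits the look to three, and the monitoring section leaves its starting patient open. The outcome of at most 1/6 is weak evidence, since the summary uses the same wording at 10 mg, where 0/3 leads directly to escalation.

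It is also fair to say that DLTs and phase II toxicities are defined differently. A DLT is a clinically significant grade 3 or 4 event not attributed to progression, intercurrent illness or concomitant medication. Phase II counts non-hematological toxicity of grade 3 or higher. The contrast of 2/6 with 4/6 is exact only where these coincide, and nothing says that the phase II rule replaces the 3+3 rule.

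Three stronger readings might be inferred, and the documents do not support them:
- That 10 mg becomes final on three patients. The escalation section orders three more there, and 2/6 DLTs at 10 mg closes the study. Calling 10 mg final can simply mean no re-escalation. Only the missing repetition remains.
- That patients 4 to 6 have no rule at all. Starting phase II monitoring with the 7th patient makes sense only if the first six are under the 3+3 rule.
- That the trial's likeliest path ends with no MTD. The gap exists right after the 0/3 cohort; six patients would accrue as enrolment at 25 mg continued. Whether 0/3 twice is likeliest depends on the rate: at 10% it is (0.531), but at 20% for both doses closure at 10 mg, with its two routes pooled, exceeds it (0.291 against 0.262).

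**Conclusion.** The point stands as a conflict between stated dose-decision rules. The outcome 0/3 at 25 mg is not covered, although the MTD definition and phase II both depend on six patients. Two or three DLTs in patients 4 to 6 then lead to different actions in different sections. The SAP repeats the escalation text and so does not resolve it; the SAP as supplied ends before toxicity monitoring.

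The uncovered outcome may be common, but the harmful sequence is uncommon. The larger values of B, 0.22 to 0.50, are conditional on 0/3 and should not be read as the share of trials affected; A × B gives that share among trials reaching 25 mg. All these probabilities rest on assumed DLT rates, independent patients, and the same events counting under both toxicity rules. The matter should be corrected because the conflict concerns patient safety and the choice of the phase II dose, and the remedy is cheap.

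**What to change.** Reconcile Selection of Patients, Dose Escalation Procedures with its summary, and the phase II toxicity monitoring section of the protocol, and the matching SAP text, so that:
- the outcome 0/3 at 25 mg has a stated next step;
- the number of patients that settles a dose is the same in the MTD definition, the decision rules and the monitoring section;
- one stated rule governs patients 4 to 6 at a level;
- the first patient for phase II toxicity monitoring is fixed to match;
- Selection of Patients and the summary agree with the escalation section on how many patients are treated at 10 mg after a fall-back.

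Which rule applies is for the clinical team. The cost is a few sentences. The maxima of 12, 22 and 25 need not change: even six patients at each level fit the 12 for one escalation (3 + 6, 6 + 6 or 3 + 6 + 3). The separate escalation for younger patients in the Inclusion Criteria is outside that count.

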## Phase II

Phase II part is a single arm study using the dosage level recommended from phase I. The patients treated at the MTD in phase I will be included in phase II part, and the sample size for phase II can be up to 22. The trial will be continuously monitored for efficacy and toxicity (non-hematological  $\geq$ grade 3). The method of Thall, Simon, and Estey will be used to perform interim efficacy and safety monitoring (15).

## **Efficacy**

The primary endpoint is the response defined as the CNS is without evidence of blast cells after four lumbar punctures with rituximab. The historical data suggested the response rate by chemotherapy (methotrexate and/or cytarabine) is about 10%. The targeted improved overall response rate is 25%, The trial will be continuously monitored. The study will be stopped early if the data suggest that:

$$\Pr(\pi > 0.1 | \text{data}) < 0.05$$

Here  $\pi$  is the response rate. That is, if at any time during the study we determine that there is a less than 5% chance that the response rate is greater than 10%, we will terminate the study. The response

rate is assumed to follow a non-informative prior of Beta (0.2, 1.8). The study will be stopped early if (The number of responders)/ (The number of patients evaluated)  $\leq 0/9$ .

Table 2: Operating characteristics for monitoring of overall response rate

| True Response Rate | Early Stopping Probability | Median Sample size (interquartile) |
|--------------------|----------------------------|------------------------------------|
| 0.05               | 0.63                       | 9 (9, 22)                          |
| 0.1                | 0.40                       | 22 (9,22)                          |
| 0.15               | 0.23                       | 22 (22,22)                         |
| 0.2                | 0.14                       | 22 (22,22)                         |
| 0.25               | 0.08                       | 22 (22,22)                         |

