##### ***Diagnosis***

Diagnosis of CNS leukemia involves assessing the cerebrospinal fluid (CSF) by lumbar puncture (LP) or intraventricular sampling. Signs and symptoms include headache, mental status changes, motor deficits, and seizures. In most patients, the CSF is abnormal (protein concentration greater than 50 mg/dL, leukocyte count greater than 4 per mm^3, and positive cytology). A positive cytology by itself is diagnostic of LMD. In leukemias and lymphomas, the yield of positive cytology following one or two lumbar punctures is approximately 70% (3).

Neuroradiographic imaging can also be involved in the diagnostic workup, to include cranial computed tomography (CT), magnetic resonance imaging (MRI), CT-myelography, and radionuclide CSF flow studies (4). However, imaging studies have a high false negative rate.

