### **Inclusion Criteria**

Patients must have relapsed or refractory CD20+ lymphoid malignancies with either documented CNS involvement or peripheral nerve infiltration.

Patients 3 years of age and older are eligible after 3 patients (age 15 or older) have been treated and did not experience a dose limiting toxicity. Patient 3 to 15 years of age will follow the dose escalation schema independent of the adults.

ECOG performance status measure will be used. (ECOG Performance Status less than or equal to 3)

Adequate liver function (bilirubin less than or equal to 3 mg/dL within 24 hours of enrollment)

Adequate renal function (serum creatinine less than or equal to 3 mg/dL within 24 hours of enrollment)

Urine pregnancy test for women of childbearing potential (defined as *not* post-menopausal for 12 consecutive months or no previous surgical sterilizations). A negative urine pregnancy test is required within 48 hours of initiating study drug.

Signed informed consent

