### **Patient Evaluation**

#### **Pre-Treatment Evaluation**

- History and physical examination, including vital signs, height, weight and performance status.
- Blood will be drawn for routine tests.
- Diagnostic lumbar puncture
- Concomitant drugs and side effects will be evaluated and recorded.

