#### **Criteria for Response**

Patients will be considered as responding to therapy if the CSF is without evidence of blast cells after four lumbar punctures with rituximab. Clinical improvement and diagnostic imaging may also be used to support a patient's response to therapy.

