### **Analysis method**

Data analysis will be performed using SAS or S-plus, as appropriate. All patients who received at least 1 dose of the agent will be included in the intent-to-treat analysis for efficacy. Demographic and disease characteristics of the patients at registration will be summarized using descriptive statistics such as mean, standard deviation (SD), median and range. Overall response rates will be presented with 95% confidence intervals. The association between response and patient and disease characteristics will be examined by two-sample t-test or Chi-square test.

The data from all patients who received the therapy during the study will be included for safety analysis. Safety data will include laboratory, physical exam, and adverse event reports on study patients. These descriptive summaries will be provided for all patients for each safety parameter by intrathecal rituximab dose #, grade, and relationship to treatment.

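### Patients with no CSF blasts at entry can count as responders, and one such patient among the first nine switches off the futility rule

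*Protocol*

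**What the plan says.** - **Endpoint.** The Protocol, under Criteria for Response, states: "Patients will be considered as responding to therapy if the CSF is without evidence of blast cells after four lumbar punctures with rituximab". The Efficacy sections of the Protocol and the SAP repeat this as the primary endpoint, with CNS in place of CSF.
- **Entry.** The Protocol, under Inclusion Criteria, states: "Patients must have relapsed or refractory CD20+ lymphoid malignancies with either documented CNS involvement or peripheral nerve infiltration". Pre-Treatment Evaluation lists a "Diagnostic lumbar puncture" but requires no particular result.
- **Analysis set.** The Protocol, under Analysis method, states: "All patients who received at least 1 dose of the agent will be included in the intent-to-treat analysis for efficacy".
- **Peripheral-nerve-only patients.** Statistical Considerations (Protocol and SAP): "There is no well-defined metric to measure response to treatment in patients with peripheral nerve involvement only". For these patients the plan is to note how they do clinically and on imaging. It expects few or none and concludes that the analysis is unaffected.
- **Benchmark and rule.** Protocol, Efficacy: "The historical data suggested the response rate by chemotherapy (methotrexate and/or cytarabine) is about 10" per cent, with no source. The target is 25%. The trial stops if the posterior probability that the response rate exceeds 10% falls below 0.05, under a Beta(0.2, 1.8) prior, and the stated boundary is 0/9.
- **Cytology yield.** The Protocol's Diagnosis section, on leukemia and lymphoma, says that "the yield of positive cytology following one or two lumbar punctures is approximately 70" per cent.

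**The concern.** The endpoint asks whether blasts are absent after treatment, not whether blasts that were present have gone. Taken together, the entry criteria, the pre-treatment work-up and the analysis set leave room for patients whose CSF has no blasts at the start. If their CSF stays negative, they meet the response definition whatever the drug does.

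A few such patients would matter little to a rule that tolerates some responders. This rule tolerates none: it stops only when nobody among the first nine has responded. At stake is whether the trial can still stop early on an inactive agent, and whether the final response rate can be read against 10% and 25% as evidence of CSF clearance.

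**Working it through.** **Inputs.** Prior Beta(0.2, 1.8), threshold 0.10, cut-off 0.05 and boundary 0/9 (Protocol, Efficacy). Maximum of 22 patients in phase II (Protocol and SAP, Phase II). The share f of enrolled patients who meet the definition with no drug effect is not in the documents. It is an assumption, shown over a range.

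**1. Reproduce the plan's boundary and Table 2.** After r responders in n patients the posterior is Beta(0.2 + r, 1.8 + n − r). The probability that the rate exceeds 0.10 is 0.0531 at 0/8 (continue) and 0.0453 at 0/9 (stop), so 0/9 is the first stopping point, as stated. Because only zero responders ever stops the trial, the stopping probability at response rate p is (1 − p)^9:

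| p | (1 − p)^9 | Table 2 |
|---|---|---|
| 0.05 | 0.630 | 0.63 |
| 0.10 | 0.387 | 0.40 |
| 0.15 | 0.232 | 0.23 |
| 0.20 | 0.134 | 0.14 |
| 0.25 | 0.075 | 0.08 |

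Table 2 is reproduced within rounding and simulation error.

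**2. Effect of one responder.** The posterior probability is 0.436 at 1/9 and 0.124 at 1/22. With one responder it would first fall below 0.05 at n = 32, beyond the maximum of 22. Any single responder among the first nine, genuine or not, therefore ends futility stopping for the rest of the trial.

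**3. Inert agent with default responses.** With true clearance of zero and a share f of default responses, the observed response rate is f. The probability of escaping the rule is 1 − (1 − f)^9:

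| f (assumed) | (1 − f)^9, stopped | 1 − (1 − f)^9, escapes |
|---|---|---|
| 0 | 1.00 | 0 |
| 0.05 | 0.63 | 0.37 |
| 0.10 | 0.39 | 0.61 |
| 0.20 | 0.13 | 0.87 |

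**4. The peripheral-nerve statement.** One peripheral-nerve-only patient without CSF blasts, if enrolled among the first nine and scored on the written definition, gives at least 1/9. By step 2, that alone switches off the rule. Expecting few such patients is therefore not enough to leave the monitoring unaffected.

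**5. Price of restricting to baseline-positive patients.** If 30% were baseline-negative (assumption), 22 × 0.7 = 15.4, so about 15 patients would be evaluable. The ninth evaluable patient would arrive at about enrolment 9/0.7 = 12.9, that is 13. The exact (Clopper-Pearson) 95% confidence interval is 10.7–50.2% at 6/22 and 7.8–55.1% at 4/15.

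**The case against.** Several points on the other side stand.

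- **The 70% yield does not give f.** A reader might infer from the Diagnosis section that up to 30% of patients will be recorded as responders without a drug effect. The documents do not support that. The figure is a diagnostic yield over one or two punctures, not a rate for this endpoint. It is not a ceiling either: if 70% is cumulative over two independent punctures, the single-puncture miss rate is √0.30 = 0.55. In the other direction, entry needs documented involvement, so some patients missed by cytology would not enrol, and later misses in patients known to be positive may be rarer. The yield shows only that negative CSF in a patient with disease is plausible.
- **The 10% may already contain default responses.** If it was measured with the same cytology in a similar population, f would be at most about 0.10, and an inert agent would be stopped with probability of at least 0.39, essentially Table 2's 10% row. The plan does not say how the 10% was measured, so this can be neither confirmed nor excluded.
- **Table 2 is not wrong.** It is correct for the response rate as observed. The sensitivity to one responder comes from the prior and the boundary, and it applies equally to an agent with a genuine 5% rate (0.37).
- **There is no success rule to breach.** One might infer that an inert agent could be declared effective once its confidence interval excludes 10%. The plan only presents a 95% interval and sets no such criterion.
- **The intent may be narrower than the text.** Criteria for Removal from Study refers to persisting blasts, which suggests that baseline blasts are presupposed. No section directs that a peripheral-nerve-only patient be scored as a CSF responder. But none excludes such a patient, and the analysis set includes everyone treated.

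The gap in the definition and its exact effect on the rule remain.

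**Conclusion.** The concern holds in this form and should be fixed. As written, the endpoint, entry criteria and analysis set allow a patient with no CSF blasts at entry to count as a responder, and one such patient among the first nine removes futility stopping through n = 22. The second part follows exactly from the stated prior and cut-off. The statement that few peripheral-nerve-only patients leave the analysis unaffected does not hold for this rule.

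How often this would happen is unknown. The escape probabilities of 0.37, 0.61 and 0.87 rest on assumed values of f and on independent patients with no true clearance. They are illustrations, not estimates for this trial.

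**What to change.** In the Protocol (Efficacy and Analysis method) and the SAP (Efficacy):

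1. Base the primary response rate and the futility rule on treated patients with blasts in the pre-treatment CSF sample.
2. Report baseline-negative and peripheral-nerve-only patients separately, for clinical and radiologic response, and keep them in the safety analysis.
3. State the 10% and 25% for that same population and endpoint, give the source of the 10%, and reconcile it with the Protocol's section on Treatment of Leptomeningeal Disease, which describes CNS clearance in a treated ALL series as high without giving a figure.
4. Report response confirmed on the next scheduled CSF sample as a sensitivity analysis only. Making it primary would be a trade-off, since its benefit depends on how far misses in consecutive samples are correlated.

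Eligibility, schedule, removal criteria, the prior and the 0/9 boundary stay as they are.

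The work is a text edit. The cost is precision and a later first futility look: under the 30% baseline-negative assumption, about 15 evaluable patients instead of 22, the first look at about enrolment 13, and an interval of 7.8–55.1% (4/15) instead of 10.7–50.2% (6/22). If nearly all enrolled patients are baseline-positive, the cost is close to nil.
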